3.6.2. Simethicone

Simethicone is an oral anti-foaming agent with a long history of use in clinical practice and diagnostics ^{96, 97, 98, 99, 100}.

3.6.2.1. Mechanism of action of Simethicone

Simethicone reduces the amount of gas in the intestine. Simethicone has surface activity and is able to reduce the surface tension at the liquid / gas interface. This leads to fusion of gas bubbles and destruction of the foam. Therefore, released gas can be absorbed or removed naturally due to intestinal motility¹⁰¹ (Instruction for medical use for Espumisan®, Appendix 1).

As suggested by Debray and co-workers over 40 years ago, Simethicone acts as a local barrier that protects the mucosa from irritants, such as hydrochloric acid, acetylsalicylic acid or bile salts ^{102, 103}. Simethicone probably interacts with endogenous surface active substances, protecting the intestinal mucosa. The effect of Simethicone is mediated by its action in the intestinal lumen, since it is not absorbed and does not have a toxic effect¹⁰⁴.

3.6.2.2. Clinical efficacy of Simethicone

Some modern randomized prospective studies have shown the efficacy of Simethicone in patients with traveler's diarrhea ¹⁰⁵ and functional dyspepsia ^{106, 107, 108, 109}. In addition, the efficacy of the drug in preparation for diagnostic procedures is well known ^{110, 111, 112, 113, 114, 115, 116, 117, 118, 119, 120, 121, 122}

According to the results of randomized, placebo-controlled studies, treatment with probiotics and Simethicone reduces the severity of flatulence and abdominal discomfort in patients with IBS to whom the diagnosis was made in line with previous versions of Rome criteria ¹²³.

Anti-foaming effect is the main mechanism of action of Simethicone. As a result, patients who received Simethicone prior to the diagnostic procedure showed improved quality of visualization

Confidential Page 37 of 94

during ultrasound examination of the gastrointestinal tract^{110, 111,112} and endoscopy ^{113, 114, 115, 116} because Simethicone reduces bubbles and foam in the intestinal lumen. Addition of Simethicone in intestinal lavage or to laxatives also reduces the foam content in the colon and residual feces; this was confirmed by colonoscopy^{117, 118, 119, 120, 121} and by ultrasound examination of rectum¹²².

A literature search revealed 13 comparative studies and 6 double-blind studies that meet modern requirements for clinical studies. More than 3,000 patients who received Simethicone in various formulations were included in these clinical studies of therapeutic efficacy of Simethicone.

According to clinical studies, the most relevant to modern requirements, the effect of Simethicone in the treatment of patients with functional dyspepsia significantly exceeds the effect of placebo, as well as the effect of cisapride, which was used as a comparator drug^{106, 107, 108, 109}.

Both functional dyspepsia and IBS are characterized by abdominal pain; however, in patients with IBS, there is also abnormal defecation pattern. Simethicone is usually prescribed to patients with IBS to reduce the feeling of bloating and flatulence¹²⁴, but there were no adequately conducted prospective comparative studies.

When analyzing the published literature data, only two studies were identified, in which 80 patients who received Simethicone and 54 patients who received placebo were included. Oswald et al. in 1961 published the results of a placebo controlled Simethicone study at a dose of 50 mg (tablets); the results showed that Simethicone was more effective than the comparators. ¹²⁵ In 1974, Weiss ¹²⁶ published a review and results of Simethicone study in 30 patients, also revealing the advantage of Simethicone. In more recent studies, the results of which are discussed below, in the section "Clinical studies of Simethicone as part of combination therapy," the efficacy and safety of Simethicone were evaluated in combination with other drugs in patients with IBS.

Urgesi R et al in 2014 published the results of a double-blind, randomized placebo -controlled study, which confirmed the efficacy of the combined use of probiotic and Simethicone. Patients were randomized to receive combination therapy with probiotic and Simethicone (n = 26) or placebo (n = 26); the duration of treatment was 4 weeks. Efficacy was evaluated at 2 weeks and 4 weeks from the start of therapy. ¹²³.

Combination therapy with probiotics and Simethicone led to improvement in the main IBS symptoms (in line with diagnostic criteria before Rome IV), such as flatulence, abdominal discomfort and altered defecation pattern. Noteworthy, significant difference was found between the test group and placebo in the degree of reduction of flatulence and abdominal discomfort. The severity of abdominal pain statistically significantly decreased in the combination therapy group as compared to the baseline. More powerful clinical studies are need to identify the differences between the treatment groups in the degree of abdominal pain reduction.

Many patients with acute diarrhea, regardless of the cause, also complain on increased gas formation, cramps, abdominal pain, bloating, abdominal distension, flatulence, nausea and vomiting. In a double-blind placebo-controlled study, Kaplan et al compared the efficacy and safety of loperamide hydrochloride and Simethicone with Simethicone monotherapy, loperamide monotherapy and placebo in patients with acute diarrhea with abdominal discomfort caused by gas formation. The duration of therapy was 48 hours. The study included 493 patients. 124 patients were randomized to the combination therapy group (loperamide 2 mg and Simethicone 125 mg), 123 patients were randomized loperamide 2 mg, 123 patients received Simethicone 125 mg, and 123 patients received placebo. After randomization, these patients received 2 tablets of the study drug, then patients took one tablet of the prescribed drug after each episode of liquid stool, up to 4 tablets for 24 hours.

The primary end points were the time until the last liquid stool and the time until resolution of abdominal discomfort disappeared. An analysis of the results revealed that patients who received the combined treatment with loperamide and Simethicone have significantly (P <0.001) shorter time to the last liquid stool and abdominal discomfort disappears more quickly in comparison with both monotherapy group and the placebo group. Simethicone in monotherapy was significantly (P <0.01) more effective than placebo in alleviating general symptoms, alleviating diarrhea,

Confidential Page 38 of 94

abdominal discomfort, reducing the number of bowel movements with a liquid stool over a period of 36-48 hours.

In 2007, Hanauer et al published the results of a multicenter, double-blind study in patients with acute diarrhea¹²⁷. The patients were randomized to receive two tablets, each contained either loperamide 2 mg and Simethicone 125 mg (n = 121), or loperamide 2 mg (n = 120), or Simethicone 125 mg (n = 123), or placebo (n = 121). The duration of therapy was 48 hours. As well, as in the study of Kaplan¹⁰⁵, the median time to the last liquid stool for group that received the combination therapy was significantly less than for loperamide, Simethicone and placebo groups (7.6 h, 11.5 h, 26.0 h and 29.4 h, respectively, p <0.0232). The time to complete resolution of discomfort was lower in the combination therapy group as compared to the monotherapy and placebo groups (all p = 0.0001).

Thus, co-administration of Simethicone and loperamide led to a more rapid resolution of acute nonspecific diarrhea and associated discomfort (abdominal pain, spasms, flatulence) in comparison with each drug as monotherapy or placebo; superiority of Simethicone monotherapy over placebo was also demonstrated 105.

Tolerability of the study treatment was good; none of the patients required rescue therapy.

Thus, a number of modern randomized prospective studies have shown efficacy of Simethicone in patients with traveler's diarrhea, functional dyspepsia. In additional, the efficacy of treatment with Simethicone during preparation to diagnostic procedures is well known.

According to randomized placebo controlled studies, therapy with a probiotic with Simethicone reduces the severity of flatulence and abdominal discomfort in patients with IBS (in line with diagnostic criteria before Rome IV).

3.6.2.3. Safety of Simethicone

Simethicone is usually well tolerated and has a favorable safety profile. No causal association of Simethicone with adverse events was found in published clinical studies. No systematic laboratory abnormalities, as well as laboratory abnormalities associated with Simethicone, have also been identified according to published data.

In 2007, Rémy Meier and Michael Steuerwald published a review of clinical studies with Simethicone and noted that the comparison of Simethicone with placebo, cisapride, loperamide, combination of loperamide with Simethicone, in terms of incidence of adverse events, serious adverse events and early withdrawals due to adverse events was in favor of Simethicone. ⁴⁰ No causal relation of Simethicone with adverse events was found in published data from clinical studies. Systematic laboratory abnormalities, as well as laboratory abnormalities associated with Simethicone, were also not detected according to published data.

According to Espumisan Instruction for use (Simethicone is the active substance), no adverse effects have been reported after treatment with this drug; some allergic reaction to the excipients drug may be expected. There is low likelihood of overdose with Simethicone. In a safety study conducted by Nair et al. In 2003, healthy volunteers received Simethicone at a dose of 30 grams per day for several days without developing adverse events and without laboratory abnormalities in biochemical parameters¹⁰⁴.

3.7. Combined use of antispasmodics and Simethicone

In patients with FBD, a smooth muscle spasm of the gastrointestinal tract has an important role in the development of a pain symptoms. Error! Bookmark not defined. Antispasmodics are included in recommendations for the treatment of IBS as first-line line for the last decades ^{1,35,36}

Simethicone is not currently included in recommendations for treatment of patients with IBS due to insufficient data from clinical studies. However, the results described above suggest that addition of Simethicone to the main therapy would be effective and would bring relief to a significant proportion of patients with FBD, because almost all of these patients suffer from flatulence.

Confidential Page 39 of 94

Combined treatment with antispasmodic alverine and simethicone has lead to decrease in pain/discomfort intensity in patients with IBS, ^{39, 128} and also has lead to improvement in quality of life. It is important to note that in one study³⁹ in which the majority of patients took antispasmodics, addition of simethicone to alverine resulted in additional statistically significant improvement in quality of life and reducing symptoms such as abdominal pain and bloating/flatulence.

In 2011, Wittmann et al. published the results of a double-blind, randomized placebocontrolled study of the efficacy and safety of the combined use of myotropic antispasmodic alverine and Simethicone in patients with IBS (in line with diagnostic criteria before Rome IV.³⁹

In this study, the patients with IBS (according to the Rome Criteria, revision III) were randomized to receive alverine citrate in combination with Simethicone or placebo. The treatment lasted 4 weeks. The primary endpoint was abdominal pain / discomfort intensity, assessed using Visual-Analogue Scale (VAS) after 4 weeks of therapy. In addition, the number of responders in both groups was compared. The response to treatment was defined as decrease in the number of points in the assessment of pain / discomfort on the VAS scale by 50% or more after 4 weeks of treatment. In the study, 207 patients were randomized to the combination therapy group and 205 patients to the placebo group. 399 (97%) patients completed the study. The results showed that the intensity of abdominal pain / discomfort after 4 weeks of therapy was significantly lower in the combination therapy group compared to the placebo group (median 40 mm versus 50 mm in the combination therapy and placebo groups, respectively, p = 0.047). In addition, the response rate to the treatment was also significantly higher in the combination therapy group compared to the placebo group (46.8% compared to 34.3%, OR = 1.3; p = 0.01). The patients who received the combined therapy significantly improved the general medical condition in comparison with patients from the placebo group.

The results on reduction in pain/discomfort after treatment with alverine and Simethicone showed that recovery rate was equal to 8; this is slightly less than the values obtained in previous studies for smooth muscles relaxants⁴⁴ In addition, an improvement in overall well-being was noted; it was significantly more pronounced in the combination therapy group as compared to the placebo group. The effect of combination therapy on abdominal distension was not evaluated. Since there is no data on the comparative efficacy of combination therapy, alverine and Simethicone in monotherapy, it is difficult to determine which component contributes mote to observed the therapeutic effect of the combination.

Thus, the use of antispasmodic combination therapy with alverine and Simethicone was effective in reducing the pain / discomfort in patients with IBS.

Ducrotte et al conducted a long (6 months of therapy) double-blind randomized study that compared the efficacy and safety of episodic use of combination therapy with alverine and Simethicone when a pain attack occurred and the standard therapy chosen by the attending doctor for each patient 128 . Patients in the combination therapy group (n = 222) were instructed to take a capsule with a combined preparation 3 times a day before meals if a pain attack occurs and until it resolves. In the control group (n = 214), the doctor chose the tactics of treatment, it was forbidden only to prescribe the combination therapy with alverine and Simethicone.

The primary endpoint in the study was the difference between groups in the change in the number of points on the questionnaire of quality of life from the initial to the end of therapy after 6 months.

Initially, the results of assessment of quality of life on a scale were comparable in both groups. Median dosing frequency in the combination therapy group was 75% days per month during the first month, 54% days per month for 2-3 months, and 45% days per month for 4-6 months. In the standard treatment group, 93.8% patients received at least one antispasmodic.

Confidential Page 40 of 94

The improvement in the quality of life after assessing by Quality of Life scale during 6 months of therapy was significantly more pronounced in the combination therapy group (13.8 versus 8.4 with a difference between 5.4 groups (95% CI: 2.3 - 8, 6; p = 0.0008. The percentage of improvement was also greater in the combined treatment group (28.5% compared to the conventional treatment group 18.6%; p = 0.04). According to the VAS score, abdominal pain decreased by 76.1% in the combination therapy group and by 59.2% in the conventional therapy group (p = 0.0001). In patients suffering from flatulence when included in the study, the severity of symptoms in the combination therapy group decreased by 76.6% compared with 57% in the standard therapy group (p < 0.0001).

Thus, the occasional use of combination therapy with alverine and Simethicone led to an improvement in the quality of life of patients with IBS (in line with diagnostic criteria before Rome IV), as well as to a reduction in the severity of symptoms, such as abdominal pain and flatulence, in comparison with standard therapy. In the comparison group, the vast majority of patients were treated with antispasmodics. Thus, addition of Simethicone to antispasmodics provides significant clinical advantage, improving the quality of life and reducing the severity of symptoms typical for FBD.

3.7.1. Conclusion on the combined use of antispasmodics and Simethicone

The use of antispasmodic combination therapy with altering and Simethicone led to a decrease in pain / discomfort in patients with IBS (in line with diagnostic criteria before Rome IV), as well as to an improvement in the quality of life of patients. Noteworthy, in one of the studies. in which the vast majority of patients received antispasmodics in the control group, addition of Simethicone to altering provided statistically significant advantage in improving the quality of life and reducing the severity of symptoms such as abdominal pain and flatulence.

[figure not shown]
Thus, addition of Simethicone to antispasmodics provides a clinically significant advantage, improving the quality of life and reducing the severity of main symptoms of FBD.

3.7.2. Approved combinations of Simethicone and antispasmodics

Fixed-dose combination, Meteospasmil, which includes altering 60 mg and Simethicone 300 mg, was approved in 1990 in Europe. The same combination of drugs was approved in the Russian Federation in 2007 (Meteospasmil). Meteospasmil is indicated for the treatment of functional disorders of the gastrointestinal tract, manifested by abdominal pain, increased gas formation, belching, nausea, constipation, diarrhea, or their alternation, as well as for preparation to X-ray, ultrasound or instrumental examination of the abdominal organs.

3.8. Fixed-dose combination Mebeverine+Simethicone

[figure not shown]
Fixed-dose combination Mebeverine + Simethicone, film-coated tablets 135 mg + 80 mg, is a new drug that contains mebeverine and Simethicone in one tablet. Currently, the drug has been

[figure not shown]
Confidential Page 41 of 94

	_	
-		
_		

Confidential Page 42 of 94

Confidential Page 43 of 94

3.8.1. Risk/benefit ratio

The study is aimed at the evaluation of comparative efficacy and safety of the fixed-dose combination of Mebeverine + Simethicone film-coated tablets 135mg + 80mg versus Duspatalin® film-coated tablets 135mg and Espumisan®, 40mg capsules (2 capsules). The study will include patients with functional diseases of the colon with abdominal pain and bloating/flatulence.

Pain in patients with functional diseases of the colon is due to the spasm of intestine smooth muscles and excessive formation of gas. Spasmolytics being used for the decades are currently included into IBS treatment guideline as the first-line therapy. In accordance with the Clinical Guideline of Russian Association of Gastroenterology and Russian Association of Coloproctology on the diagnosis and treatment of irritable bowel syndrome, pain relief in IBS patients can be achieved with the use of various types of spasmolytics, i.e. blockers of M-cholinergic receptors, sodium and calcium channel blockers (Clinical Guideline of Russian Association of Gastroenterology, 2014). According to the IBS Treatment Guideline of the World Gastroenterology Association, the first-line therapy of this disease also includes spasmolytics, such as mebeverine, otilonium, hyoscine, cimetropium, pinaverium, and dicyclomine

Simethicone is not included into IBS treatment guidelines due to the absence of sufficient clinical data, although it is suggested that its addition to the basic therapy would be effective and alleviating in many patients, as far as almost all of FBD patients experience flatulence according to the data published. Many authors emphasize a strong negative effect of flatulence in the compromised well-being of FBD patients, because this symptom changes the intensity: it is the most prominent during the daytime, worsens after meal and generally abates at night^{21,37,38}. Simethicone, as an antifoaming agent, helps to reduce flatulence, discomfort and abdominal pain due to the improved gas evacuation from the GI tract^{39,40}.

The contribution of each component will be proven in a clinical study by studying co primary endpoint that will provide data on the pharmacodynamic effects of the components, as well as by studying the relevant secondary endpoints.

Confidential Page 44 of 94

The risk associated with the use of Mebeverine in clinical studies is considered low, comparable to placebo, and is mostly limited to rare anaphylactic reactions, mainly, but not exclusively, limited to the skin, such as urticaria, angioedema, facial edema, exanthema, and hypersensitivity, including anaphylactic reactions. The frequency of anaphylactic reactions due to mebeverine cannot be assessed, because no such reactions were reported in the clinical studies. Anaphylactic reactions may be caused by any drug and are not considered an important risk during its use.

Data of clinical safety studies show the comparability of safety profile of mebeverine to placebo, therefore, mebeverine can be considered to possess a favourable safety and tolerability profile for symptomatic treatment of FBD if used in accordance with the therapeutic guidelines.

The most common post-marketing adverse reactions were the gastrointestinal tract disorders (26.3%), skin and subcutaneous tissues disorders (22.0%), general disorders and injection site conditions (20.2%), as well as the nervous system disorders (16.1%).⁹²

Common GIT reactions and multiple symptoms from other system and organ classes are not considered related to mebeverine and considered to be generally due to the underlying disease. IBS is often accompanied with other pain syndromes, besides gastrointestinal ones, such as back pain and chest pain. Moreover, IBS is frequently associated with psychiatric and neurological symptoms.

Therefore, if properly used, mebeverine generally demonstrates a favourable benefit-to-risk ratio.

The risk associated with the use of Simethicone is extremely low. The drug is not absorbed in the gastrointestinal tract, has a local effect, and is eliminated unchanged. In the published clinical studies data, a causal relation of adverse events to Simethicone has not been identified. According to the published data, no systemic laboratory abnormalities or laboratory abnormalities related to Simethicone have been observed.

According to the prescribing information for Espumisan® (simethicone), no adverse drug reactions have been reported; allergic reactions to the drug excepients are possible.

Risks associated with rescue medication drotaverin is also low.

The instruction on medical application for the No-spa® (drotaverin) is applied in Appendix 1.

Drotaverine is an antispasmodic drug which is a phosphodiesterase IV inhibitor, it increases the cyclic adenosine monophosphate, inactivates the kinase of light myosin chain which leads to smooth muscles relaxation. Its effect is shown within 45-60 minutes and lasts for 8-10 hours. The product will be allowed only as a rescue therapy to relief intensive pain episode in a dose of 80 mg 1 - 3 times a day during one day after the episode.

Contraindications to drotaverine intake are hypersensitivity, severe renal failure, severe hepatic failure, severe heart failure, hereditary galactose or fructose intolerance, total lactase deficiency, sucrase-isomaltose insufficiency, glucose-galactose malabsorption syndrome.

The side effects of drotaverin are rare, among them are: head ache, dizziness, insomnia, palpitation, hypotension, nausea, constipation, allergic reactions.

3.8.2. Clinical program for fixed dose combination Mebeverine+Simethicone development

The clinical program for the development of a fixed-dose combination of Mebeverine + Simethicone film-coated tablets 135 mg + 80 mg consists of a study of the pharmacokinetics and comparative bioavailability in healthy volunteers that confirmed the bioequivalence of the fixed-dose combination versus Duspatalin®, and a study of the efficacy and safety in patients with

Confidential Page 45 of 94

functional bowel disorders followed by intestinal pain and bloating. The parallel three-group study of efficacy and safety is planned to compare, according to the EAEU Guidelines for the Development of Fixed-Dose Combinations, the reduction in abdominal pain and bloating, as well as the rate of adverse events, during treatment the fixed-dose combination of Mebeverine + Simethicone versus Duspatalin® and Espumisan® as a monotherapy.

Confidential Page 46 of 94

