3.5. Study design rationale

This is a multicenter randomized open-label comparative clinical phase III study in parallel groups for assessment of efficacy and safety of Mebeverine+Simethicone fixed-dose combination versus Duspatalin® (mebeverine) and versus Espumisan® (simethicone) in patients with functional bowel disorders with abdominal pain and excess gas formation.

3.5.1. Assessment of superior efficacy of Mebeverine+Simethicone fixed-dose combination versus any of it's mono-component.

Investigated fixed-dose combination Mebeverine+Simethicone include well known drugs with favorable safety profile; these drugs have long history of successful use in clinical practice.

The bioequivalence of the FDC Mebeverine+Simethicone and Duspatalin® was confirmed in phase I clinical study.

In line with EEU Guideline on fixed dose combinations preclinical and clinical development the randomized controlled clinical study in three groups in purpose to evaluate the superioriority of efficacy and acceptability of safety profile of the FDC Mebeverine+Simethicone versus Duspatalin® (mebeverine) and versus Espumisan® (simethicone) is planned.

According to EMA Guidelines for development of pain medicines,⁴⁷ visual analogue scales (VAS), numeric rating scales (NRS) and verbal rating scales (VRS) are used to assess pain in clinical studies. To confirm the efficacy of investigational product over time as a primary endpoint, it is recommended to use mean pain intensity differences from baseline (PID). Moreover, it is indicated that for long-term studies it is recommended to use as a primary endpoint a parameter such as the average pain intensity per week in a daily measurement compared to the baseline value. This Guidelines also recommend the use of Sum of Pain Intensity Differences (SPID) and its associated area under the pain intensity-time curve in most cases, but this parameter is intended to assess the effect over time of classic analgesics, after a single dose of anaesthetic. In the case of functional bowel disorders, this parameter does not seem applicable, as the pain is wave-like and may not occur every day. None of the components of the fixed combination of Mebeverine+Simethicone is a classic analgesic.

For the self assessment of bloating/flatulence intensity by patient the numeric rating scale (NRS-11) will also be used. Such self assessment of bloating/flatulence intensity is being performed in clinical studies in patients with FBD. 46

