9.8.2. Safety end points analysis

The safety sample will be used for the analysis of the safety and tolerability data.

Treatment Emergent Adverse Events (TEAEs) including AE and SAE will be presented by frequencies (number of patients with AEs and number of events) and are summarized by unique treatment (Mebeverine+Simethicone, Duspatali®, Espumisan®), primary System Organ Class (SOC) and Preferred terms (PT) and relation to the study drug and severity. Severity and drugevent relationship of the treatment emergent AEs are summarized separately.

Laboratory values and vital signs by visit and their changes from baseline will be summarized in tables of descriptive statistics. Abnormal values (according to the reference ranges) will be presented in frequency tables (low, normal and high values).

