4.3 Safety analysis

The Safety subject sample will be used for the analysis of the safety data. In addition to this, three treatment groups will be used: "Mebeverine+Simethicone fixed-dose combination", "Espumisan® (simethicone)" and "Duspatalin® (mebeverin)".

The gap period is 7 days for adverse events, 7 days for vital signs, laboratory measurements and concomitant medications.

The following dictionaries are used for coding of medical terms:

Medical term	Dictionary	Version
Concomitant medications	WHO DDE	March 2020, or later
Adverse events	MedDRA	23.1
Medical histories	MedDRA	23.1

Treatment Emergent Adverse Events

An AE that starts during a unique treatment or that already exists before the start of that unique treatment but worsens during the treatment or post-treatment period (if no longer than 7 days after last dose of respective treatment) will be considered as treatment emergent for that unique treatment.

The following unique treatments are distinguished: Mebeverine + Simethicone, 135 mg+80 mg, three times a day; Duspatalin 135 mg three times a day; Espumisan, 80 mg (2 capsules 40 mg) three times a day. AEs will be reported on a per-subject basis, i.e., counting subjects rather than events. This means that if a subject suffers the same AEs repeatedly during the applicable study or treatment period, the event will be counted only once for that period. Repeated events per subject will be summarized according to the following rule: if a subject suffered the same AE more than once, the event will be assigned the worst severity, the closest relationship to the study drug and the earliest starting date. Only treatment emergent AEs (TEAE) will be reported. In the listings, however, all occurrences of the AEs will be presented.

For each unique treatment, TEAES will be summarized by MedDRA primary system organ class (SOC), high level term (HLT) within primary SOC and preferred term (PT) within HLT and primary SOC. Severity and drug-event relationship of adverse events are summarized separately.

In the listings, all occurrences of AEs will be presented together with all relevant information from the eCRFs. In addition, TEAEs will be flagged. Start and end day of the AE and the day of last dose of study drug will be also presented, relative to the start day of the treatment under which is started or worsened and relative to start of any study drug.

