Safety variables will be summarized descriptively per treatment. Quantitative variables will be described by n, arithmetic mean, SD, minimum and maximum. Qualitative variables will be described by frequency tables containing counts and percentages.

For each unique treatment, treatment emergent AEs will be summarized per primary SOC, per HLT by primary SOC and per PT by HLT and primary SOC. Severity and drug-event relationship of treatment emergent AEs are summarized separately.

Laboratory values, vital signs and their changes from baseline will be summarized by visit in tables of descriptive statistics. Abnormal values (according to the reference ranges) will be presented in frequency tables (low, normal and high values).

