4.3.7 Adverse Events

Source: AET001, AET002, AET003, AET005, AET006, AET007, AET008, AET009, AET010, AEL002, AEL008, AEL009, AEL010, AEL011, AEL012, AEL013

Adverse Events will be presented in tables grouped by treatment, SOCs, HLTs, PTs and sorted by descending order of total incidence. SOCs, HLTs, PTs will be coded by the Medical Dictionary for Regulatory Activities version 23.1 ENG (MedDRA 23.1 ENG). In addition to this, the information will be reported on a by-subject data listing.

Adverse Events (TEAEs) started after the last administration of study drug but within the Gap Period after the last administration will also be attributed to the Treatment Period. For more detailed information see Module 2.

An intergroup comparison for two treatment groups is not planned.

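### The protocol says adverse event rates on the combination will be compared with each single drug, but only per-arm counts and percentages are planned, with no between-arm difference or interval

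*Protocol*

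**What the plan says.** **Purpose and objectives.** Protocol 3.8.2 describes the trial as planned to compare "the reduction in abdominal pain and bloating, as well as the rate of adverse events, during treatment the fixed-dose combination" with each monotherapy. Protocol 3.5.1 gives the aim as to "evaluate the superioriority of efficacy and acceptability of safety profile of the FDC" against each single drug. Protocol 2.2 and SAP 3.3 list the incidence and severity of adverse events among the parameters to be evaluated for the combination versus Duspatalin and versus Espumisan.

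**Analysis.** Under protocol 9.8.2, treatment-emergent adverse events (TEAEs) "will be presented by frequencies (number of patients with AEs and number of events") by treatment, with no difference, test or interval. SAP 4.3 follows: "Safety variables will be summarized descriptively per treatment", and "Qualitative variables will be described by frequency tables containing counts and percentages". TEAEs are tabulated by system organ class, high level term and preferred term. Severity and relationship to study drug are summarised separately. SAP 4.3.7 adds: "An intergroup comparison for two treatment groups is not planned". The same sentence appears in SAP 4.3.2 (medical history) and 4.3.9 (concomitant medication).

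**The concern.** The purpose and objectives name a comparison of adverse event incidence between randomised arms, and the analysis sections of both documents do not carry it out. For binary efficacy endpoints, protocol 9.7.4 promises a 95% confidence interval for the difference in proportions. Adverse event incidence is also a proportion and is also listed under versus each comparator, yet it gets no such interval.

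What is at stake is how the safety result will be read. If two arms show similar percentages, the report will not say whether the data exclude a meaningful excess on the combination or are simply too sparse to show one. If the percentages differ, it will not say whether the gap is within chance.

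**Working it through.** **1. Is there a planned figure to reproduce?** Not for safety. Neither document gives a hypothesis, margin, power or precision for adverse events. The only sample size is for the primary efficacy endpoint (protocol 9.2: difference 1.0, SD 2.5, two-sided alpha 0.05, power 90%):

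- n per arm = 2 × (1.960 + 1.282)² × 2.5² / 1.0² ≈ 131.3, so 132. This matches the protocol.
- With 15% drop-out: 132 / 0.85 = 155.3, which the protocol gives as about 155.

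The safety sample is everyone randomised who took at least one dose, so 155 per arm is close to its expected size.

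**2. Precision of the missing contrast.** With equal true rates p in both arms, the Wald 95% half-width is 1.96 × √(2p(1 − p)/155). The Newcombe values use the nearest whole count out of 155.

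| Rate p | Source | Wald | Newcombe (count per arm) |
|---|---|---|---|
| 5% | assumed | ±4.9 points | ±5.3 (8) |
| 10% | assumed | ±6.7 | ±7.0 (16) |
| 20% | assumed | ±8.9 | ±8.9 (31) |
| 35% | protocol 3.6.1.3 | ±10.6 | ±10.5 (54) |

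Example at 35%: 2 × 0.35 × 0.65 / 155 = 0.002935; square root 0.0542; × 1.96 = 0.106.

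If only 132 per arm contributed, the Wald range from 5% to 35% would be ±5.3 to ±11.5 points.

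**3. The anchor.** The 35.0% is 474/1354 in the pooled mebeverine studies of 1968 to 2011 and covers all adverse events. The 4.5% in the same paragraph (61/1354) counts only events judged drug-related, so it is not used as an all-cause rate. Neither is a forecast for this trial.

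**4. What an interval adds.** Take invented counts of 24/155 (15.5%) on the combination and 15/155 (9.7%) on a comparator. The difference is +5.8 points, Newcombe 95% CI −1.7 to +13.3. The risk ratio is 1.6, 95% CI 0.87 to 2.93. The data would fit no difference, and also more than a doubling. The two percentages alone do not show that.

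**5. Two wording conflicts found on the way.** SAP 4.3.7 refers to two groups in a three-arm trial. SAP 4.3 says "AEs will be reported on a per-subject basis, i.e., counting subjects rather than events", whereas protocol 9.8.2 promises both patients and events.

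**The case against.** The best defence is that the SAP follows the protocol's own analysis section. Protocol 9.8.2 is descriptive too, and the clearest contrary sentence, in 3.8.2, sits in a section on the clinical programme and sets no hypothesis, margin or method. Setting three randomised arms side by side is a weak but legitimate form of comparison, and any reader with the counts can work out an interval. The sentence in 4.3.7 also looks like template text. Much of this stands: it rules out a simple protocol-against-SAP conflict and any demand for formal testing. It does not remove the mismatch with the objectives, which both documents state.

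A reader might infer more than the documents support:

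- **That safety gets no estimate at all.** Percentages per arm are incidence estimates, and they are planned regardless of relatedness. Only the between-arm difference and its interval are missing.
- **That the trial cannot answer its safety question.** The information will be reported. What is not shown is how precisely it answers the question.
- **That investigators will push gastrointestinal events towards unrelated.** Protocol 3.8.1 does say "Common GIT reactions and multiple symptoms from other system and organ classes are not considered related to mebeverine", but this describes past experience and is not an instruction for classifying events here. Such a drift is possible, but nothing in the documents shows that it will happen. It is a reason to count events regardless of relatedness, not a finding.

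A further limit is that the trial is open-label. An all-cause contrast does not depend on causality judgement, but it does depend on reporting by patients and investigators who know the treatment. A confidence interval does not cover that bias.

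**Conclusion.** The concern holds in a limited form. The stated purpose and secondary objectives call for adverse event incidence on the combination to be set against each single drug. Both analysis sections stop at per-arm summaries, and SAP 4.3.7 expressly declines the comparison. The omitted uncertainty is about ±5 to ±11 points for adverse event rates of 5% to 35%. This assumes about 155 treated patients per arm and similar rates in the arms; the 5% is assumed and the 35% is historical. The efficacy analysis is unaffected, and the per-arm safety data will be reported as planned. The change is still worth making, because it serves a stated objective at little cost.

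**What to change.** In SAP 4.3.7, replace the sentence declining an intergroup comparison with the following:

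- For the combination minus Duspatalin and the combination minus Espumisan, present the risk difference with a 95% confidence interval (Newcombe or Miettinen-Nurminen), without p-values.
- Do this for (a) any TEAE, (b) any TEAE in the gastrointestinal disorders system organ class regardless of relatedness, (c) serious adverse events, and (d) TEAEs leading to discontinuation.
- Label the intervals descriptive and unadjusted for multiplicity, and state that open-label reporting can bias them.
- Add a pooled hypersensitivity category only if its preferred terms are fixed before database lock.

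Correct the reference to two treatment groups wherever it occurs, and settle whether event counts are reported alongside patient counts. If the sponsor prefers to keep safety purely by arm, the minimum is to reword protocol 3.8.2 and the objectives to say so.

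The cost is a SAP wording change and one table from data already collected. The downside is a few unadjusted intervals that could be over-read, which the labelling addresses.
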